Method: After their Well Check Visit with their pediatrician, adolescents will be recruited virtually or in-person to complete a screening survey about substance use. Participants who are ineligible to complete the study because they did not use substances or have friends that use substances in the past year will receive the recommended reinforcing message for abstaining from substance use such as “You’ve made a smart decision not to use alcohol or drugs” to reinforce choice (adapted from the Alcohol Screening and Brief Intervention for Youth⁶³). This “screening out” procedure will allow for adolescent substance non-use to be reinforced in the recommended manner to save time for providers by providing evidence-based care. Eligible participants (and their guardian) will be invited to meet with a research assistant either in person at the clinic, by phone, or in

a video conference meeting to discuss the research and obtain consent. While discussing informed consent, participants and their guardians will be informed of the sensitive nature of the prevention program and that the adolescent will complete the brief survey and then research procedures. Both the adolescent and guardian will be informed that if the adolescent discloses a SA history as a child that has not been previously reported to the appropriate officials (Department of Social Services or Law Enforcement depending on the perpetrator), a report will need to be made prior to the adolescent and guardian leaving the clinic. Both the adolescent and guardian will be informed that if the adolescent discloses imminent risk of suicide and the adolescent is not willing to agree to a safety plan, a mental health professional will need to conduct an exam to determine if hospitalization is needed.

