After consenting to the prevention program and completing the baseline survey, the adolescent will be randomized to receive the interactive online prevention program (15 minutes) or no intervention. All participants will then be contacted to complete 1-, 3-, and 6-month follow-up assessments. Participants will receive a \$5 gift card for screening for the study, \$30 gift card for completing the baseline survey up to the point of randomization (plus \$10 for completing the intervention if randomized to that condition), \$40 gift card for the 1-month follow-up, \$45 gift card for the 3-month, and \$50 gift card for the 6-month. Participants may also receive partial payment for the follow-up surveys based on the percentage of the survey they complete. They will also receive a \$5 bonus for completing each survey within a week of the date it was sent, and a \$10 bonus if they complete all the surveys. Additionally, participants randomized to the intervention group will receive an additional \$10.

The research team will observe restrictions imposed by Georgia State University and relevant government or public health authorities in the conduct of research activities.

5. Study Design

A. Organizational

The Principal Investigator of the overall study is [name] and is housed at Georgia State University (GSU). This study is funded by a NIDA career development award to GSU and all funds will go through GSU.

B. Setting and location:

Study procedures will take place at GSU and recruitment will occur at two sites: in the Old Fourth Ward Pediatrics clinic in Atlanta, Georgia and at the Medical College of Georgia-Augusta University Children's Hospital of Georgia in Augusta, Georgia.

Adolescents will either complete the consent, baseline survey, and intervention at their primary care clinic or they will complete those study activities online in a private location of their choosing. All participants will complete the follow-up surveys at 1 month, 3 months, and 6 months online in a private location of their choosing. When completing data surveys and/or the intervention remotely, we will ensure that they are in a private space in these ways:

- 1) displaying a reminder screen at the beginning of all surveys and the intervention that this should be completed in a private location
- 2) displaying a reminder screen to close the browser at the end

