For adolescents under 18 who are eligible for the intervention, the guardian and adolescent will go through informed consent (guardian) and assent (adolescent under 18) after taking the screening survey (see Parental Consent, 18 Year Old Consent, and Assent Forms). While discussing informed consent, participants and their guardian will be informed of the sensitive nature of the prevention program and that the adolescent will complete the prevention program online. Both the adolescent and guardian will be informed that if the adolescent discloses a SA history, a trained research staff will contact them to report the SA to the appropriate location (Department of Social Services or Law Enforcement depending on the perpetrator) and to provide any needed referrals for treatment. After guardian consents and adolescent assents to the prevention program, the adolescent will complete the study procedures in private. Although guardians will be informed that they might be contacted to help remind their child to complete the surveys. This will be discussed with the guardian during the consent process.

[figure not shown]
For adolescents 18 years of age who are eligible for the intervention, they will go through informed consent after taking the screening survey (see 18 Year Old Consent Form). While discussing informed consent, participants will be informed of the sensitive nature of the prevention program and that they will complete the prevention program online. The adolescent will be informed that if they disclose a SA history, a trained research staff will contact them to report the SA to the appropriate location (Department of Social Services or Law Enforcement depending on the perpetrator) and to provide any needed referrals for treatment.

If possible, the consent procedures will happen in-person at the doctor's office immediately after the teen's clinic visit. Otherwise, consent will happen virtually either through video conferencing (e.g., WebEx or Zoom) on the computer located at the clinic

or by phone after the patient has left the clinic. If consent occurs via video (e.g., Zoom or Webex) or by phone, the teen and their guardian will be directed to open the study website on an internet browser, where there will be online consent and assent forms. The research team will obtain an e-signature for consent through the online form. No teen under 18 will be allowed to participate in the study without their parent's consent.

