All participants will receive referral information pertinent to treatment of substance use disorders, mental health and physical problems subsequent to SA victimization, treatment for SA perpetration, and STI testing recommendations.

Figure 1. Virtual and In-Person Recruitment, Consent, and Data Collection Procedures for Teen Well Check

F. Virtual or In-Person Field Methods:

If eligible and consented/assented for research, adolescents will complete a Baseline Survey and (if randomized to experimental condition) the intervention in privacy. Throughout the online intervention, the adolescent will have access to a research assistant (virtually by phone/text or in-person) to answer any questions that arise.

Participants complete the prevention program, which includes intervention content provided online regarding substance use, sexual assault, and sexual risk behaviors. All informed consent, baseline assessment, and the intervention (if randomized to the program) procedures will take approximately 1 hour to complete. Adolescents will be paid \$5 for screening for the study whether they are eligible or not. If they are eligible, adolescents will receive a \$30 Walmart e-gift card for participating in the baseline portion of the study (plus \$10 for completing the intervention if randomized to that condition). They will complete online follow-up surveys (see “1 Month Follow-up Survey,” “3-Month Follow up Survey,” and “6-Month Follow up Survey”) one-, three-, and six-months after participating in the baseline procedures. They will be paid a \$40 Walmart e-gift card for the one-month follow-up survey, a \$45 Walmart e-gift card for the three-month follow-up survey, and a \$50 Walmart e-gift card for the six-month follow-up survey. Participants may also receive partial payment for the follow-up surveys based on the percentage of the survey they complete. All of the follow-up surveys will take approximately 30 minutes to complete.

6. Potential Risks/Discomforts

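### Section 5.E says every family will be told the adolescent completes the prevention program, but only those randomised to it will do so

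*Combined protocol and SAP*

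**What the plan says.** Section 5.E describes the consent conversation in two paragraphs.

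- For adolescents under 18, participants and the guardian will be "informed of the sensitive nature of the prevention program and that the adolescent will complete the prevention program online".
- For 18-year-olds, participants will be "informed of the sensitive nature of the prevention program and that they will complete the prevention program online".

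The under-18 paragraph also describes agreement as agreement to the program: "After guardian consents and adolescent assents to the prevention program, the adolescent will complete the study procedures in private".

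Section 4-2 (Method) sets out the design. The step before allocation is worded "After consenting to the prevention program and completing the baseline survey", and then "the adolescent will be randomized to receive the interactive online prevention program (15 minutes) or no intervention". Section 5.F (Field Methods) matches that design: "adolescents will complete a Baseline Survey and (if randomized to experimental condition) the intervention in privacy". Section 8 lists the \$10 program payment only for those randomised to the intervention.

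Section 4-2 also gives its own account of the consent discussion. There, families are told of the program's sensitive nature and that "the adolescent will complete the brief survey and then research procedures".

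**The concern.** Being assigned by chance, possibly to receive nothing, is a basic part of what a family agrees to in this trial, and most of those agreeing will be minors with a guardian. The section that defines the consent conversation states the opposite of what will happen to the control arm. Payment also depends on allocation, since the additional \$10 goes only to those who complete the program.

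There is a statistical side as well. The comparator is open and untreated, and outcomes are self-reported. Controls who had been led to expect the program could be more inclined to drop out, or could answer differently, once they learn that they will have surveys only. Retention is one of the feasibility criteria in Section 10, and the secondary comparisons use those self-reports. Avoidable disappointment confined to one arm is therefore worth removing.

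**Working it through.** No arithmetic applies. The check sets the passages side by side.

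1. **Timing.** Section 4-2 places consent and the baseline survey before randomisation. Every family therefore has the consent conversation before allocation is known, and whatever 5.E scripts is said to future controls too.

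2. **What is promised.** Both 5.E paragraphs state that the adolescent will complete the program. Neither has an *if randomised* qualifier, and neither mentions chance allocation or a no-intervention arm.

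3. **What is delivered.** Sections 4-2, 5.F and 8 all make the program conditional on randomisation. The 5.E statement is true for the program arm and untrue for the other.

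4. **Is the promise met later?** No section offers controls the program after follow-up. All participants receive referral information (Section 5.E) and a Resource Sheet (Section 6), but neither is the program.

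5. **Does another section supply the missing statement?** Section 4-2's account of the consent discussion is neutral: it does not promise the program, but it does not mention randomisation either. Section 6 says families are told about mandated reporting, the right to decline and the right to stop. Section 12 says they are told about risks and adverse events. None of these mentions allocation.

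6. **Is the wording consistent elsewhere?** Not fully. Section 5.F has the conditional phrase, but its next paragraph opens by saying, without condition, that participants complete the program, and then restores the condition one sentence later. Agreement to the program, as distinct from agreement to the trial, appears in both Section 4-2 and Section 5.E, while Section 5.F speaks of consent or assent for research.

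Sections 4-2, 5.E and 5.F therefore disagree about what consent covers. The two 5.E paragraphs contradict the design outright.

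**The case against.** The strongest reply is that 5.E is not the consent document. It points to parental, 18-year-old and assent forms, Section 5.D points to recruitment scripts, and Figure 1 is said to diagram the consent process. None of these can be seen here, and that is not a fault in the plan. They may explain randomisation fully. This stands. It limits the point to what the protocol says the discussion will contain. It does not remove the point: if the forms are right, the protocol disagrees with its own forms and 5.E still needs correcting.

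A second reply is that 5.E is not a full list of consent content. It is silent on payment, for example, so silence on allocation proves little. That is fair for the silence. It does not answer the positive statement that the adolescent will complete the program.

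A third reply is that this is loose shorthand, as the slip in Section 5.F suggests. That is probably how it arose. But 5.E is where staff would look for what to tell families, in person, by video or by phone, for recruitment at two sites, and the qualifier is absent from both paragraphs.

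Finally, an open no-intervention arm can disappoint controls however consent is worded. Here the item withheld lasts 15 minutes, and controls get the same follow-up payments and bonuses. Section 10 already rules out efficacy conclusions. All of this stands, and it is why the effect on the data is described as plausible only.

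**Conclusion.** The contradiction is certain as a matter of text. Read as written, the consent discussion in 5.E would be untrue for anyone allocated to no intervention. It should be corrected before the section is relied on. It changes no sample size, error rate or analysis.

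A reader might infer three stronger things that the documents do not support.

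- *That controls will in fact be misinformed.* This would need the forms and scripts, which are not available.
- *That control-arm retention will suffer by a calculable amount.* The allocation ratio is not stated. Section 10 gives 70 as the number meeting criteria out of 250 screened, while Section 4-2 speaks of 250 recruited for the trial, so the size of the control arm cannot be derived. The 80% retention target is for participants overall, not by arm. Nothing gives dropout by arm or links dropout to consent wording.
- *That the recruitment result would be inflated.* Section 10 judges recruitment by numbers screened and numbers meeting criteria, and neither depends on consent.

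**What to change.** In both 5.E paragraphs, replace the unconditional statement with wording to this effect: *the adolescent will be assigned by chance either to the online program or to no program (surveys and Resource Sheet only), and will be asked to complete the 1-, 3- and 6-month surveys in either case.*

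Then align the related text:

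- Section 4-2: the description of the consent discussion, and the phrase that describes consent as being to the program.
- Section 5.E: the sentence in which the guardian consents and the adolescent assents to the program.
- Section 5.F: the sentence that has participants completing the program without condition.

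Confirm that the consent and assent forms and the recruitment scripts say the same.

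The cost is a wording amendment through the IRB. A few more families may decline once the no-intervention arm is stated plainly.

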The two potential risks to participants that may be associated with involvement in the study include: 1) potential threats to confidentiality, particularly with regard to reporting sexual assault and reporting of imminent suicide risk without agreeing to a safety plan; and 2) potential embarrassment or distress from responding to questions or engaging in the prevention program targeting sensitive topics including substance use, sexual assault, and sexual risk behaviors. These risks are discussed in greater detail below. In addition, although not a risk specifically linked with participating in the study, the vulnerability of adolescents who have experienced sexual assault necessitate consideration of procedures in the cases of psychiatric emergencies (e.g., suicidal attempts). These considerations are noted here and in the following Protection Against Risk section.

First, regarding potential threats to confidentiality, there may be emotional and/or legal consequences if personal information obtained during the assessment is released to outside parties. That is, mandatory reporting laws necessitate that new disclosures (i.e., previously unreported) of qualifying incidents of child abuse (including SA of someone under the age of 18 years old), be reported to the Department of Social Services/DSS (when perpetrator of abuse is in a caretaking position) or the local law enforcement agency (when perpetrator of abuse is in a non-caretaking position). Reports to such agencies may result in DSS involvement with the family, removal of family members or child from the home, or criminal charges/arrests. With regard to likelihood of this threat to confidentiality in relation to child abuse reporting, sexual assault history will be initially assessed through the assessment during the feasibility trial prior to beginning the prevention program. Participants will be informed of these risks of mandatory reporting laws prior to completing the assessments. A research assistant and licensed psychologist (e.g., P.I. [name]) will be immediately informed if an adolescent discloses a sexual assault victimization.

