Our proposed methodology was developed in order to balance the safety of human subjects with the ability to acquire accurate data. We have used similar procedures in both local and national studies. We ultimately chose a tablet-based intervention because individuals are more likely to disclose information about sensitive topics like sexual assault, alcohol use, and sexual risk behaviors in self-report measures than when asked by a person. Therefore, including the tablet-based intervention rather than an in-person intervention will increase the likelihood of disclosures. However, this is balanced with the human subjects concern and ethical concern of mandatory reporting laws. It is essential to ensure that children are safe from child abuse, and sexual assault is a form of sexual abuse. We have included mandatory reporting within these procedures to ensure that participants within this study are protected from future harm. However, it is notable that in the National Survey on Adolescents, which several of the mentors on the current project oversaw the Child in Danger protocol, out of the approximately 3600 youth confidentiality was broken in less than 5 cases total. Previous and current studies conducted by the research team have revealed that adolescents do in fact still disclose sexual assaults even with being informed that it is mandatory that we report the incident. However, it is possible that some adolescents will not disclose sexual assault if they are informed in will be reported to the authorities if disclosed. Because of this, we ensured that all participants will receive the same information and resources despite their reported histories to ensure that they receive the best care possible. It is a potential limitation that the sexual assault victimization experiences will likely be under representative of the actual rates in the population being observed.

Similarly, if an adolescent is threatening to hurt her/himself or someone else, confidentiality may have to be broken to make a report to the guardian and/or necessary authorities. Given that suicidality is common among child sexual abuse victims, while not a direct risk of the study, it is an important issue to assess and monitor closely with participants. Procedures for assessing and addressing suicide attempts are addressed in the following Protection Against Risk section.

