To protect against violations of confidentiality: (a) a federal certificate of confidentiality has been automatically granted because it is study funded by NIDA to render the data immune from subpoena (due to the sensitivity of some of the data that we are collecting - e.g., self-reports of drug use and SA - and the potential legal jeopardy faced by some of the participants); while aware of the ambiguities about the reach of the certificates, we are convinced that they are the best protection available for confidentiality of research data; (b) all staff will sign confidentiality agreements, and our training sessions will emphasize the critical importance of confidentiality; (c) all hard copies of data will be kept and locked within the research office; (d) the computer containing the data will be password-protected as a security precaution to eliminate unauthorized access; (e) all digital data including survey responses will be stored on the encrypted GSU Enterprise Dropbox account that requires dual-identity log-in and is only available to members of this study team.

Regarding the risks of breaking confidentiality due to mandated reporting laws: a) adolescents and guardians (if under the age of 18) will be informed of the risks during the consent process, and continually reminded of the risks throughout the study (e.g., at each assessment time-point); and b) when a question arises about whether a situation falls under a mandated reporting law, the research personnel and/or a licensed psychologist will be alerted immediately by text message and email. The PI will make all final decisions about whether a mandated report must be made on behalf of a study participant. If a mandated report is required, guardians and/or adolescents will be encouraged to make the report themselves (e.g., from the office within the primary care clinic), such that confidentiality is not broken by the project staff. If the guardian or adolescent refuses to make the report, then the research personnel will be required to make the report. This leads to very limited instances where confidentiality is actually broken by staff. The proposed mentorship team has extensive experience in dealing with these issues with trauma-exposed child populations.

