For participants enrolled in the study, in any circumstances where a research assistant or a licensed psychologist is concerned regarding suicidal ideation or attempt, the P.I. will be contacted immediately. All research staff will have a cell phone number where the P.I. will be available 24 hours 7 days a week. In rare instances where she cannot be reached, a licensed psychologist will serve as a back-up. [name] will ensure research assistants are well-trained in assessing distress and suicidality (intent, plan, etc) using a Safety Plan that includes the Linehan risk assessment and management protocol (LRAMP) (see "TWC Suicide Safety Plan Revised 041321"). In circumstances where adolescents in either condition express suicidal ideation and are sincerely willing to contract for safety (i.e., will agree to keep her/himself safe), the guardian will not be informed. The safety plan—detailing what to do and whom to speak with if ideation should occur—will be discussed with all participating adolescents who screen positive for suicidality, including specifics on how to access 24-hour care for suicidality via dialing 9- 1-1 and/or going to the closest emergency department (research staff will help families determine this location) when a licensed psychologist and/or supervisor is not available. Thus, a 24-hour safety plan is in place, including access to medical care 24 hours per day. Further, any participant in which it is deemed that medication is warranted will be referred to a hospital or community-based psychiatrist for such services and monitoring. Suicidal risk factors - including suicidal ideation, intent, plan, and means - will continue to be assessed on an ongoing basis throughout the adolescents' participation in the study via the baseline and follow-up surveys.

If a participant is deemed at risk for suicide and the adolescent will not contract for safety, or has made any indication of acute suicidal risk, the guardian will be informed immediately and the adolescent will be assessed by local emergency department for possible inpatient hospitalization.

In all surveys, if a teen reports a sexual assault or suicidal ideation while completing the online survey, a notification will be made to [name] automatically. No matter the teen's responses, all teens will receive information for the suicide hotline and information about how to report a sexual assault if they have experienced one as a child. However,

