For participants enrolled in the study, in any circumstances where the study staff is concerned regarding suicidal or homicidal ideation or attempt, or SA perpetration against a minor, s/he will immediately contact [name], who is a licensed psychologist in South Carolina (License No. PSY.1417). [name] will assess safety and provide instructions to the study staff to address any risks. [name] will ensure that the study staff are well-trained in assessing distress and suicidality (ideation, intent, plan, etc). In circumstances where participants express suicidal ideation and are sincerely willing to contract for safety (i.e., will agree to keep her/himself safe), a plan will be made and carefully monitored. If a participant is deemed at-risk for suicide and will not contract for safety or has made a suicidal behavior or attempt, the participant will be assessed by a local emergency department for possible inpatient hospitalization. [name] or trained research staff will also ensure that participants who present with risk for suicidal or homicidal ideation are well educated on how to access 24-hour emergency care (through 9-1-1 or going to the local Emergency Department). [name] will be on-call for study therapists, 24 hours per day, 7 days per week.

B. Procedures for Monitoring Safety of Data

Regarding data management and storage, all data will be collected using computerized self-report questionnaires. Only participants' study identification codes will be inputted computer-based databases. The codes that link the name of the participant and the study ID will be kept confidential by [name] in a secured cabinet. The data will be imported directly into a password-protected SPSS data file stored on the GSU server. The server is protected by the GSU network, and a secured log-in is required from all users. All research personnel collecting and manipulating data will have completed a Human Subjects Research Training and will meet weekly with [name] or a postdoctoral fellow in the lab to ensure strict compliance with the DSM plan. Only study personnel (candidate, research staff, and mentorship team) will have access to data. No data will be released to other agencies unless participants consent to release.

Adverse Events

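### Both consent statements in Section 5.E attach a report to any disclosed sexual assault history, which is broader than the reporting rule in Sections 4-2 and 6.

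*Combined protocol and SAP*

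**What the plan says.** Section 5.E (Informed Consent Process) has two parallel statements. For adolescents under 18 it says "Both the adolescent and guardian will be informed that if the adolescent discloses a SA history, a trained research staff will contact them", and goes on to say that the contact is to report the assault and to give any needed referrals. For 18-year-olds, who consent alone, it says "The adolescent will be informed that if they disclose a SA history, a trained research staff will contact them to report the SA". In both, the report goes to Social Services or law enforcement, depending on the perpetrator.

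Section 4-2 (Pilot Feasibility Trial, Method) covers the same consent discussion, but there a report follows "if the adolescent discloses a SA history as a child that has not been previously reported to the appropriate officials".

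Section 6 (Potential Risks/Discomforts) gives the mandated-reporting rule as covering "new disclosures (i.e., previously unreported) of qualifying incidents of child abuse (including SA of someone under the age of 18 years old"; the parenthesis closes after those words. Its procedure starts only when a disclosure requires reporting. Under Protection Against Risks it adds "The PI will make all final decisions about whether a mandated report must be made on behalf of a study participant", and it gives all teens "information about how to report a sexual assault if they have experienced one as a child".

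On the effect of such a warning, Section 6 says "it is possible that some adolescents will not disclose sexual assault if they are informed in will be reported to the authorities if disclosed".

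**The concern.** Section 6 names threats to confidentiality, with SA reporting singled out, as one of the study's two main risks. It lists possible consequences of a report that include removal from the home and arrest. The consent section is where that risk is explained, and its stated trigger is wider than the rule the study says it will follow.

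An adolescent weighing whether to disclose would be told that a report will follow in cases where the plan requires none. If that adolescent stays silent, the automatic notification is not sent and staff do not make contact within 24 hours. What is at stake is accurate consent and access to personal follow-up.

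**Working it through.** The plan gives no figure on this point and no arithmetic applies. The check is a comparison of the statements.

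| Place | Limited to assaults not already reported? | Limited by age? |
|---|---|---|
| 5.E, under 18 with guardian | No | No |
| 5.E, age 18 | No | No |
| 4-2, consent discussion | Yes | Yes (as a child) |
| 6, mandated-reporting rule | Yes | Yes (victim under 18) |

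**Step 1: does anything in the 5.E sentences narrow the trigger?** No. The reference to the perpetrator decides only which agency receives the report. The word *needed* qualifies the referrals, not the report.

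**Step 2: do Sections 4-2 and 6 agree with each other?** Yes in substance. Section 4-2 speaks of childhood and Section 6 supplies the age. Section 6 is the better source for a correction because it refers to the victim's age. That keeps "SA perpetration against a minor", which Section 12.A treats as a safety concern, within the trigger. Section 4-2's phrase covers only the participant's own childhood.

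**Step 3: for whom do 5.E and the rule differ?**
- Unreported assault of someone under 18: no difference where the incident qualifies under Section 6.
- Assault already reported: 5.E announces a report, while 4-2 and 6 do not. This can arise at consent in both age groups.
- Assault at 18 or later: 5.E announces a report, while 4-2 and 6 do not. At consent this can arise only for 18-year-olds. Someone who enrols under 18 can reach this position only by turning 18 during the 6-month follow-up.

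**Step 4: does the difference have a consequence in the plan's own terms?** Section 6 accepts that a reporting warning may suppress disclosure. It also says that any assault reported in a survey triggers an automatic notification and staff contact within 24 hours, whether or not a mandated report is due. An over-broad warning can therefore cost a participant that contact when no report was required.

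**Step 5: how many people?** The documents give no age distribution, no count of assaults at 18 or later, and no count of assaults already reported. No number can be derived.

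**The case against.** The best defence is that 5.E is a short summary and the protocol should be read as a whole. Section 4-2 has the correct limits for the same discussion. Section 6 says participants are told of mandated-reporting risks before the assessments, directly after stating the qualified rule, and are reminded at each time point. Section 5.E points to separate consent and assent forms, which are what participants read. The error is also in the cautious direction, and Section 6 reports that adolescents do still disclose when told that reporting is mandatory.

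Much of this stands. Some participants may hear the correct rule, and the harm is possible rather than shown. It does not make 5.E accurate: a participant could be given two different rules on a principal risk, and Section 6 itself concedes that warning has a cost.

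A reader might infer four stronger things that the documents do not support:
- *Wrong reports will be filed.* Section 6 makes reporting conditional and leaves the final decision to the principal investigator.
- *Participants were in fact misinformed.* The forms are not in the public file and may carry the limits.
- *The SA outcome comparison is biased.* Consent comes before randomization and nothing suggests that the warning differs by arm. Section 6 already expects victimization to be under-represented.
- *Remote disclosures have no procedure, because 4-2 speaks of a report before leaving the clinic.* Section 6 supplies one: notification, contact within 24 hours, and a report by the researcher where required.

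**Conclusion.** The point holds as an inconsistency in the protocol text. Both consent statements in 5.E omit two limits that Sections 4-2 and 6 state. Followed as written, they over-warn participants whose assault was already reported or occurred at 18 or later.

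The mismatch itself is certain from the text. Any effect on disclosure rests on Section 6's own concession and on the assumption that staff or forms follow 5.E. Its size is unknown. Three things contain it: the principal investigator's review, the resource and referral information given to everyone, and the other places where the rule is explained. Nothing here bears on sample size, outcome data or the planned analysis. It should be corrected because it concerns one of the plan's two named risks and is cheap to put right.

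**What to change.** In both 5.E statements, replace the open-ended trigger with the one in Section 6, for example: *a qualifying incident of child abuse that has not been reported before, including sexual assault of a person under 18*.

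Add a sentence saying that any other disclosed assault leads to the existing follow-up contact within 24 hours and to resource and referral information, but not to a mandated report. This is needed because the 5.E sentence also carries the offer of referrals, which would otherwise be narrowed along with the report. It should promise no more than that: Section 6 ties staff-delivered referrals to disclosures that require reporting, and other participants receive the follow-up contact and the general materials.

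Then check the parental consent, 18-year-old consent and assent forms, and the survey reminders, for the same wording.

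The cost is one IRB wording amendment, extended to the forms and reminders if they match 5.E. Data collection, sample size and analysis do not change.
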